### 3.5. Clinical Trial Rationale

Immune checkpoint inhibitors therapy in ER+ breast cancer has not been encouraging thus far. However, strategically combining molecularly-targeted agents that may increase immune recognition of tumor cells through enhanced antigen presentation and/or increase T cell homing may increase ICI response. This clinical trial will examine these different strategies in a genotype-specific (mutually exclusive and across all ER+ breast cancers) manner:

- □ MEK inhibition (MEKi) in *TP53*-mutant ER+ breast cancer: ER+ tumors with MAPK pathway activation exhibit metastatic phenotypes of luminal B (more often *TP53*-mutated) disease. In luminal-like breast cancer models, a combination of MEKi and PD-1/PD-L1 ICI induces profound anti-tumor effects, in part by blocking na"ve CD8+ T cell priming, increasing neoantigen-specific CD8+ T effector cells in the tumor microenvironment (TME), and by protecting CD8+TIL cytotoxicity through inhibition of apoptosis driven by chronic TCR stimulation.
- □ MDM2 antagonism in *TP53*-wt ER+ breast cancer: MDM2 antagonists both de-repress wt-p53, not mutant p53 and prevent proteosomal degradation of *TP53*-wt allowing wt-p53 to activate its transcriptional program of senescence (termed Senescence-Associated Secretory Program [SASP]) The SASP recruits immune cells through secretion of T cell homing chemokines.

We hypothesize that approaches which enhance antigen presentation (MHC-I/II) or PD-L1 through MEK inhibition, or enhance expression of T-cell recruiting chemokines via MDM2 inhibition, will increase activated tumor-specific CD8+ T cells in the TME and augment the efficacy of the anti-PD-L1 mAb Atezolizumab in ER+ mBC.

Correlative studies using tumor tissue and blood will determine whether the respective molecularly-targeted agent enhances CD8+ T cells in the tumor microenvironment, enhances antigen presentation, and/or increases T cell homing chemokines. These molecular endpoints will be tested for their association with patient-specific clinical outcome. If these strategies indeed modify the tumor microenvironment as predicted, we may turn immune-unresponsive tumors like ER+BC into immune-responsive to anti-PD-L1 therapies. This would have major implications on the use of anti-PD-L1 in other "cold" solid tumors as well, by defining one or more approaches to turn "non-inflamed into inflamed tumors". Thus, the breadth of existing preclinical data and the timing are highly supportive for this trial.

# 3.6. Correlative Science Background

A number of correlatives for response to immunotherapies have been proposed using retrospective data analyses, but almost none of them have been conclusively shown to associate with PD-1/PD-L1 targeted therapy response in well-controlled clinical trials to date, including PD-L1. Other proposed biomarkers have been tumor infiltrating lymphocytes (TILs)57,58, CD8+ T cells, mutation burden, neoantigen burden. It will be important to collect these data to determine their utility in breast cancer patients, and how combinations of molecularly-targeted therapies affect these correlatives.

MEK signaling pathway. Our previous preclinical studies have clearly demonstrated a connection between enhanced MHC-I/MHC-II and PD-L1 expression following MEK inhibition and improved response to anti-PD-L1 immunotherapy. Furthermore, in melanoma, we have demonstrated an association between MHC-II expression and clinical outcome including objective response, progression-free survival, and overall survival. This finding has now been confirmed in over 100 clinical specimens. MEK inhibition sensitizes tumors to PD-L1 inhibition by upregulating MHC-I and MHC-II antigen presentation while leaving the PD-1/PD-L1 interaction as the 'gatekeeper' of a full anti-tumor response. Upregulation of CD8, MHC-I, and PD-L1 was observed with cobimetinib in Phase I-treated colorectal cancer patients. Thus, we have reason to hypothesize that MEK inhibition will alter the expression of MHC-I and II, and that this will be correlated to clinical response in patients.

Senescence-associated transcriptional programs. The work of our colleagues 65-67 have demonstrated that senescence-associated cytokines can recruit T cells to the tumor microenvironment and facilitate T cell responses. This program can in part be activated by senesence-inducing therapies that stabilize p53. Nutlin, or idasanutlin (MDM2 antagonsts) are an effective way to activate senescence-associated transcriptional programs. Thus, our correlatives in the Idasanutlin arm will be aimed at ascertaining whether Idasanutlin activates these transcriptional programs in p53-wildtype tumors, whether this associates with increased T cell homing, and finally, whether these effects correlate with patient response.

### 3.6.1. Proposed Correlative Studies

### Tissue and blood

The comprehensive correlative studies proposed within this trial were designed to provide further understanding of both tumor and immune factors that predict response or resistance. Our main goals are to determine the therapeutic predictive role of the biomarkers proposed on clinical outcome, and to determine if the cfDNA results will discriminate pseudoprogression from true progression. Results will be compared before and after single agent therapy, and immune cell phenotyping in blood will be evaluated during therapy. The following correlative studies will be included:

1. TIL analysis from H&E

- 2. CD8, CD4, Foxp3, PD-L1, MHC-I and II expression via multiplexed IHC
- 3. DNA exomes: to identify neoantigens, neoantigen load and mutations/copy number changes.
- 4. HLA haplotyping for neoantigen prediction
- 5. RNA-seq: to identify gene expression patterns for the following purposes:
  - a. Molecular subtype (PAM50)
  - b. MEK activation signatures
  - c. Immune cell composition by CIBERSORT
  - d. SASP gene expression profile (CCL5, CXCL9,10,11,13)
  - e. Expression level of potential neoantigens
- 6. CyTOF for T cell subsets in peripheral blood

1.	Collection of plasma for future cfDNA based analyses.
W€	e expect Cobimetinib treatment to result in the following changes in paired tumor biopsies: DECREASE in MEK activation signature (transcriptionally defined  ), demonstrating on-target pharmacodynamics activity of Cobimetinib. This will be performed as we have previously published  . A paired T-test (or non-parametric equivalent) will be used to test the hypothesis.
	INCREASE in TILs, CD8,CD4, PD-L1, MHC-I and MHC-II IHC expression, which we expect will also be associated with a higher likelihood of response. A paired T-test (or non-parametric equivalent) in patients WITH clinical benefit versus patients WITHOUT clinical benefit will be used.
•	INCREASE in IFNγ-response transcriptional signatures  , which is a marker of both the activity of the local immune environment, and a marker of the robustness of the tumor response to IFNγ.
	·
۱۸/۵	e expect Idasanutlin treatment to result in the following changes in paired tumor biopsies:
	INCREASE in mRNA expression of CCL5, CXCL9, CXCL10, CXCL11, CXCL13. A paired T-
	test (or non-parametric equivalent) in patients WITH clinical benefit versus patients WITHOUT clinical benefit will be used. We will correct for multiple comparisons with a Bonferroni adjustment.
□ At	clinical benefit will be used. We will correct for multiple comparisons with a Bonferroni adjustment.  INCREASE in mRNA expression of SASP/SIRS and senescence-associated markers  INCREASE in TILs, CD8, and CD4 IHC expression, which we expect will also be associated with a higher likelihood of response. A paired T-test (or non-parametric equivalent) in patients
□ At	clinical benefit will be used. We will correct for multiple comparisons with a Bonferroni adjustment.  INCREASE in mRNA expression of SASP/SIRS and senescence-associated markers INCREASE in TILs, CD8, and CD4 IHC expression, which we expect will also be associated with a higher likelihood of response. A paired T-test (or non-parametric equivalent) in patients WITH clinical benefit versus patients WITHOUT clinical benefit will be used.  PRE-Bx or POST-Bx, we expect the following associations in both arms (Cobimetinib and

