#### 24.2. Phase II Trial of Atezolizumab with Cobimetinib or Idasanutlin Study Design

Subsequent to the completion of the Phase Ib dose escalation portion for the Idasanutlin arm of this study, the Phase II portion of the Idasanutlin arm of this trial will open. The Phase II portion of the Cobimetinin arm will start once the study is activated, as no Phase I is necessary for that combination. Patients will be allocated based on TP53 mutational status and treated with a 15 day lead-in of Cobimetinib or Idasanutlin, followed by combination therapy with Atezolizumab until progressive disease or intolerable toxicity. Tumor tissue and blood will be obtained at study start and before initiation of Atezolizumab. Additional blood samples will be obtained after the first cycle of combination therapy and at disease progression.

The primary endpoint of this study is Progression-Free Survival (PFS); imaging will be performed at 8-week intervals. To observe a definitive outcome (success or failure), we will define treatment success as being progression-free at 16 weeks when the subjects will have the second imaging. Patients will be followed for a minimum of 12 months from time of study initiation, and their actual progression-free survival time will be recorded. There will be two treatment groups; however, these two groups will not be compared, rather each arm will be compared to historic control.

Secondary endpoints include ORR defined by iRecist, Clinical benefit rate (lack of disease progression at 6 months), Duration of Response (DOR), Overall Response Rate (ORR by RECIST 1.1), and percentage of patients alive (OS) at 12 months, and will be similarly summarized with 95% CI by arm. Patients will be followed for a minimum of 12 months from time of study initiation.

Safety will be evaluated by estimating the percentage of patients who experience a clinically relevant toxicity (both patient and physician reported) for each arm. Additionally, continuous monitoring for toxicity will be employed.

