# 24.3.4. Correlative Science Endpoints

Each biomarker will be compared to each clinical endpoint, particularly the primary endpoint of overall response rate, overall response by iRecist, and PFS. These exploratory analyses will be performed using the baseline biopsy, and also using correlative science assay values obtained from the Cycle 1 Day 1 time point biopsy.

Biomarkers will be categorized as continuous variables (gene expression values, expression signatures, IHC staining intensity, FAC based cell type counts, Neoantigen burden, etc.), or as dichotomous variables (somatic mutation in gene X yes or no, DNA copy number change Y, etc.). Many continuous variable scores will be also examined as dichotomous, but given the exploratory nature of these the precise cut points are not yet determined. Some specific assays are listed below, and when it says response it is understood to mean testing each assay result versus all response endpoints, both using the baseline biopsy and the C1/intermediate time biopsy.

A paired t-test (or the non-parametric equivalent if needed) will be used to determine if the proposed endpoints are significantly increased in paired biopsy in either arm. In exploratory analyses, patients will also be stratified by clinical response to determine if the change in endpoint is associated with patient-specific clinical response.

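### Section 3.6.1 names a paired t-test to compare patients with and without clinical benefit, which are independent groups, and Section 24.3.4 names no valid test in its place

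*Combined protocol and SAP*

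**What the plan says.** Section 3.6.1 (Proposed Correlative Studies, Tissue and blood) lists the biomarker changes expected between the PRE and POST biopsies and attaches a test to several of them.

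- **Cobimetinib, MEK activation signature:** "A paired T-test (or non-parametric equivalent) will be used to test the hypothesis". This is a within-patient comparison, and pairing is right.
- **Cobimetinib, TILs, CD8, CD4, PD-L1, MHC-I and MHC-II:** the increase is expected to go with a higher likelihood of response, and then "A paired T-test (or non-parametric equivalent) in patients WITH clinical benefit versus patients WITHOUT clinical benefit will be used".
- **Idasanutlin, chemokine mRNA (CCL5, CXCL9, 10, 11, 13):** again a paired "test (or non-parametric equivalent) in patients WITH clinical benefit versus patients WITHOUT clinical benefit will be used", here with a Bonferroni adjustment.
- **Idasanutlin, TILs, CD8 and CD4:** the same rule, without a stated adjustment.

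Section 24.2 defines the grouping variable: "Clinical benefit rate (lack of disease progression at 6 months").

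Section 24.3.4 (Correlative Science Endpoints) says the paired t-test, or its non-parametric equivalent, "will be used to determine if the proposed endpoints are significantly increased in paired biopsy in either arm". It then adds: "In exploratory analyses, patients will also be stratified by clinical response to determine if the change in endpoint is associated with patient-specific clinical response". No test is named for that second step.

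**The concern.** A paired test needs two values that belong together, such as PRE and POST from one patient. Each patient either has clinical benefit or does not, and no matching of one group to the other is described. As written, the test does not fit the comparison.

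The wording can be read in two ways, and neither answers the question asked. Pairing patients across groups has no basis in the design. Running a PRE/POST paired test within each group shows whether each group changed, but not whether the change is related to benefit. If one result is significant and the other is not, it is easy to report that the marker moved in one group only, and such a contrast often arises when the true change is the same in both.

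Section 3.6.1 names the predictive role of these biomarkers as a main aim of the correlative studies, and fresh paired biopsies are taken to supply the data.

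**Working it through.** The plan gives no sample size, power, alpha, SD or effect size for this comparison, so there is no stated figure to reproduce. What follows is an illustration.

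**Inputs from the documents**
- Maximum of 33 patients per arm (Section 24.3.1).
- Target hazard 0.0433 per week and 35% progression-free at 24 weeks; historical control 13% at 24 weeks (Section 24.3.1).

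**Assumptions not in the documents**
- Two-sided alpha 0.05, unadjusted.
- All 33 pairs usable.
- Normal within-patient changes with SD 1.
- The same true mean change *d* in both groups, *d* = 0.3, 0.5 or 0.8 SD, so no association with benefit.
- Benefit/no-benefit splits of 8/25, 12/21 and 16/17.

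**Step 1: likely group sizes.** Under the target, exp(−0.0433 × 24) = 0.354 and 33 × 0.354 = 11.7, so about 12 versus 21. Under the historical median of 8 weeks, 0.5³ = 0.125 and 33 × 0.125 = 4.1, so about 4 versus 29. Unequal groups are to be expected.

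**Step 2: literal pairing across groups.** With 12 versus 21 the paired statistic cannot be formed. If 12 arbitrary pairs are forced, simulated power for a true 1-SD difference in change is about 60%. A Welch test on all 33 has about 75%.

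**Step 3: a paired test inside each group.** Let *a* and *b* be the probabilities of significance in the benefit and no-benefit groups. Each is the noncentral-t power with n − 1 degrees of freedom and noncentrality d√n. Then:

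- benefit group only = a(1 − b)
- no-benefit group only = b(1 − a)
- one group only = the sum of the two

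Example, 12/21 and d = 0.5: a = 0.353, b = 0.587. Benefit only = 0.353 × 0.413 = 0.146. No-benefit only = 0.587 × 0.647 = 0.380. Sum = 0.526. A simulation of 20,000 trials gave 0.529.

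| Split | d (SD) | Benefit only | No-benefit only | One group only |
|---|---|---|---|---|
| 8/25 | 0.3 | 8.0% | 26.7% | 34.7% |
| 8/25 | 0.5 | 7.7% | 51.4% | 59.1% |
| 8/25 | 0.8 | 1.5% | 48.8% | 50.3% |
| 12/21 | 0.3 | 11.7% | 21.7% | 33.5% |
| 12/21 | 0.5 | 14.6% | 38.0% | 52.6% |
| 12/21 | 0.8 | 4.5% | 26.8% | 31.4% |
| 16/17 | 0.3 | 15.9% | 17.0% | 33.0% |
| 16/17 | 0.5 | 23.7% | 26.3% | 49.9% |
| 16/17 | 0.8 | 10.9% | 13.2% | 24.1% |

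**Step 4: a two-sample Welch test on POST minus PRE.** Simulated under the same conditions, it rejects in about 5% of trials at each of the three splits. With only 4 versus 29 it rejects in about 6%, which favours a rank-sum or permutation test there.

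**Step 5: outside the 0.3 to 0.8 SD band.** For the same splits, one-group-only significance is 9.5% at d = 0 and 1% to 17% at d = 1.2. The band covers the region where the problem is large.

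**The case against.** The best defence is that the word paired describes the biopsies. Both lists in Section 3.6.1 are introduced as changes in paired tumor biopsies, so benefit may be only the grouping. Section 24.3.4 separates the two steps and asks about the association of the change with response, which is the right question. Nothing in the plan says that p-values from two groups will be contrasted. All of this stands: Section 24.3.4 is an omission rather than another instance of the error, and the contrast of p-values is a risk left open by the wording rather than a stated procedure. It does not rescue Section 3.6.1, because even on the charitable reading no test of the difference in change is named. The text available breaks off in the list of associations expected in both arms, so this statement covers the readable text only.

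The size can also be challenged. Paired biopsies depend on consent, an accessible lesion and sample adequacy, so 33 usable pairs is an upper limit. The effect sizes are chosen, and the chemokine tests would use a stricter alpha. These are fair limits on the illustration.

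Two stronger readings are tempting and not supported. A reader might infer that the flaw mainly produces false claims of change in benefiting patients only. That pattern occurs in 1.5% to 24% of trials here; the larger no-benefit group is more often the one that reaches significance, which would argue against the protocol's hypothesis. A reader might also infer that a main goal of the trial is at risk. The goal is one of the correlative studies, Section 24.3.4 calls the response-stratified analyses exploratory, and the objectives table places correlation with outcome under exploratory.

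**Conclusion.** The point holds: the test stated three times in Section 3.6.1 does not suit two independent groups, and Section 24.3.4 does not correct it. If the rule is applied as separate paired tests, significance in one group only occurs in 24% to 59% of trials with no true association, against about 5% for a two-sample test on the change. Those figures rest on the assumed alpha, effect sizes, splits and 33 usable pairs, and they count both directions.

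The reach is limited to the correlative analyses by clinical benefit or response. The 16-week PFS decision is unaffected, and so are the within-arm PRE/POST tests, where pairing is correct. The change should be made before these analyses are run, but the point does not threaten the trial's main conclusion.

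**What to change.** 1. Keep the paired t-test, or its non-parametric equivalent, for PRE/POST change within each arm.
2. In the three places in Section 3.6.1, replace the paired test for benefit versus no benefit with a Welch two-sample t-test or Wilcoxon rank-sum test on each patient's PRE-to-POST change. Use the rank-sum or a permutation test if the benefit group is very small. A linear model of POST on benefit group, adjusted for PRE, is an alternative.
3. Name the same test in Section 24.3.4 for the association of change with response.
4. Apply the Bonferroni adjustment where the protocol states it, to the chemokine comparisons. The plan does not state it for the other two sets of markers.

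The cost is wording in two sections. No further patients, samples or visits are needed.

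Suggested text: *For each biomarker, the change from PRE to POST will be computed per patient and compared between patients with and without clinical benefit by a Welch t-test or a Wilcoxon rank-sum test; the paired test is reserved for change within an arm.*

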# 3.7. Investigational Agents

#### 3.7.1 Cobimetinib

Cobimetinib (GDC-0973) is a potent and highly selective inhibitor of MEK1/2, which is a MAPK kinase that activates ERK1/2. Inhibition of the RAS/RAF/MEK/ERK pathway affects tumor-cell proliferation and survival. Cobimetinib is a next-generation inhibitor of MEK1/2 with the previous generation represented by the comparator compound PD0325901 (PD901; Pfizer). Observations from the clinical experience with PD032590172 indicate a significant occurrence of AEs in the central nervous system (CNS) that may be mechanistically related to the RAS/RAF/MEK/ERK signaling pathway in the brain. Therefore, Cobimetinib was selected for possessing anti-tumor activity while sparing significant brain exposure.

Cobimetinib is currently approved, in combination with vemurafenib as a treatment for adult patients with unresectable or metastatic BRAFV600 mutation-positive melanoma who have been diagnosed with the cobas® 4800 BRAF V600 Mutation Test in a number of countries worldwide, including the United States, Canada, members of the European Union, and several other countries worldwide.

### 3.7.1.1 Clinical experience with Cobimetinib

Please refer to Cobimetinib Investigator's Brochure for full safety profile of cobimetinib. Study MEK4592g is a multicenter, Phase I, non-randomized, open-label, dose-escalation study. The study consisted of five treatment stages:

- □ Stage I: Dose-escalation cohorts; patients were treated on a 21 days on, 7 days off (21/7) schedule to determine the maximal tolerated dose (MTD). The MTD for the 21/7 schedule was found to be 60 mg.
- □ Stage IA: Dose-escalation cohorts; patients were treated on a 14 days on, 14 days off (14/14) schedule to determine the MTD on an alternate dosing regimen. The MTD for the 14/14 schedule was found to be 100 mg.
- Stage II: Expansion cohort with the MTD determined in Stage I (60 mg gd 21/7) in approximately 20 patients using fluorodeoxyglucose Positron Emission Tomography (FDG-PET) scans of avid tumors that harbored a BRAF, NRAS, or KRAS mutation and with FDG-PET-avid disease.
- Stage IIA: Expansion cohort with the MTD determined in Stage IA (100 mg gd 14/14) in approximately 20 patients with FDG-PET-avid tumors that harbored a BRAF, NRAS, or KRAS mutation.
- □ Stage III: A dedicated DDI study at the MTD determined in Stage I (60 mg qd 21/7) in approximately 20 patients with solid tumors.

The primary objectives of Stages I, IA, II, and IIA of this study were to evaluate the safety and tolerability of Cobimetinib administered orally as repeated doses in patients with solid tumors and to determine the MTD of daily oral administration of Cobimetinib in patients with solid tumors. The primary objective of Stage III of this study was to evaluate the possible effect of Cobimetinib on the pharmacokinetics of dextromethorphan and midazolam. Study MEK4592g has been completed; a total of 115 subjects were treated.

#### 3.7.1.2 Dose-Limiting Toxicities

Four DLTs were observed in Stage I (21/7 dosing schedule) of Study MEK4592g. At the 40-mg dose level, a DLT of Grade 4 hepatic encephalopathy was reported, which resolved following lactulose therapy, routine supportive care, and discontinuation of Cobimetinib. At the 60-mg dose

level, a DLT of Grade 3 rash was reported that improved with skin toxicity management and drug holiday. At the 80-mg dose level, two DLTs were reported: Grade 3 diarrhea despite treatment with anti-diarrheal medications and Grade 3 rash. Two DLTs were observed in Stage IA (14/14 dosing schedule) of Study MEK4592g. At the 125-mg dose level, 1 patient had Grade 3 rash and another had Grade 3 blurred vision associated with neurosensory detachment of the retina.

